## **I. Introduction**

The purpose of the statistical analysis plan (SAP) is to describe the procedures, statistical methods, and planned analyses that will be used to analyze and report results for the study. This SAP includes the details of study sample size calculation and statistical methods for analyses of primary outcome and secondary outcomes.

This study is a double-blind, parallel-assigned, randomized, prospective controlled trial (Samsung Medical Center IRB protocol No. 2020-11-016) “A randomized clinical trial of simplified dietary education versus intensive dietary education on nutritional status after gastrectomy (SING study)”.

The SING study is divided into two separate study.

- I. Study including only patients who underwent subtotal gastrectomy**
- II. Study including only patients who underwent total gastrectomy**

Patient enrollment, data cleaning, and statistical analysis will be conducted separately in each study. This SAP is the plan for the study including only patients who underwent subtotal gastrectomy. This will be done regardless of the total gastrectomy study.

## **II. Study objectives**

### **1. Primary objective**

To evaluate a difference for the percent of weight loss (%) at 12 months after surgery between the simple nutrition counseling and the intensive nutrition counseling group for early stage (IA or IB).

### **2. Secondary objectives**

- 1) Nutritional parameters, Patient-Generated Subjective Global Assessment (PG-SGA)
- 2) Intake (kcal, protein) and eating habits (meal frequency/meal speed) assessed by 24-hour dietary recall.
- 3) Albumin (Unit: g/dL)
- 4) Hemoglobin (Unit: g/dL)
- 5) Iron panel [Total Iron-Binding Capacity (TIBC) (Unit:  $\mu$ g/dL), Ferritin (Unit: ng/mL)]
- 6) Absolute lymphocyte count (ALC) (Unit:  $10^3/\mu$ L)
- 7) Vitamin B12 (Unit: pg/mL)
- 8) Homocysteine (Unit:  $\mu$ mol/L)
- 9) Quality of life using the European Quality of Life questionnaire (EQ-5D)

### **III. Study populations**

#### **1. Inclusion criteria**

- 1) Histologically confirmed gastric cancer
- 2) Patients who were diagnosed as T1N0, T1N1, or T2N0 by preoperative CT scan and pathologically confirmed after gastric resection (AJCC 8th classification)
- 3) Tumors located in the antrum, angle, lower body, or mid-body of the stomach
- 4) No evidence of metastasis from other cancers
- 5) Age between 20 and 75 years
- 6) Patients who have not previously received chemotherapy or radiation therapy, and who have not undergone gastric resection
- 7) Patients with appropriate physical function based on blood tests:
  - (a) WBC  $3000/\text{mm}^3 - 12,000/\text{mm}^3$ ,
  - (b) serum hemoglobin  $> 8.0 \text{ g/dL}$ ,
  - (c) serum platelets  $> 100,000/\text{mm}^3$ ,
  - (d) serum AST  $< 100 \text{ IU/L}$ ,
  - (e) serum ALT  $< 100 \text{ IU/L}$ ,
  - (f) total bilirubin  $< 2.0 \text{ mg/dL}$ ,
- 8) Patients who have signed informed consent

## **2. Exclusion criteria**

- 1) Active synchronous or metachronous malignancy (within 5 years prior to enrollment), excluding carcinoma in situ lesions (lesions equal to intraepithelial or intramucosal cancer)
- 2) Presence of residual gastric cancer
- 3) T3, T4 stage according to preoperative staging
- 4) N2 or higher according to CT scan or pathological findings (presence of 3 or more metastatic lymph nodes)
- 5) Histologically rare variants of gastric cancer, such as adenosquamous, hepatoid, squamous cell, undifferentiated, and neuroendocrine carcinoma, according to the WHO classification
- 6) Pregnant or breast feeding women
- 7) Individuals with diagnosed mental illness according to medical records
- 8) Individuals with uncontrolled angina or a history of myocardial infarction within the past 6 months
- 9) Individuals with uncontrolled hypertension or with chronic kidney or liver disease
- 10) Individuals with diabetes requiring insulin therapy
- 11) Individuals with severe respiratory diseases requiring continuous oxygen therapy
- 12) Individuals who have undergone previous abdominal surgery
- 13) Individuals who have experienced complications after surgery

### **3. Definition of population for analysis**

#### **1) Full Analysis Set (FA set)**

We will evaluate the primary outcome “percent of weight loss (%) at 12 months after surgery between the simple nutrition counseling and the intensive nutrition counseling group” in the FAS population. In the FAS population, all randomized subjects are included, except following subjects.

- ① Subjects who do not meet the inclusion/exclusion criteria
- ② Subjects who have never received the nutrition counseling during the study period
- ③ Subjects who did not provide any data after baseline
- ④ Subjects diagnosed with other severe diseases affecting weight or receiving additional treatment (ex. Surgery, chemotherapy, etc.) after enrollment

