#### **2) Per-Protocol Set (PP set)**

PPS consists of data from subjects included in FAS who received all nutrition counseling and completed the study per protocol without major violation.

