## **V. Data Analysis Plan**

The Full Analysis Set will be used for the primary efficacy analyses, and the Per-Protocol set will be used for supportive efficacy analyses.

The statistical methods of characteristics will be determined according to the type of variables. Continuous variables will be given as mean  $\pm$  standard deviation or median (interquartile range, IQR) and compared with a Student's t-test or Wilcoxon rank-sum test, depending on the normality of the distribution. For categorical variables, comparisons between groups will be summarized as frequency and percentile, and performed using a Chi-squared test or Fisher's exact test, as appropriate. To assess the association between two continuous variables, the correlation analysis will be performed and presented with scatter plots. In addition to, the standardized mean difference (SMD) will be calculated to estimate the difference for the mean values between two groups.

The primary objective of this study is to clarify the difference for the percent of weight loss (%) at 12 months after surgery between the simple nutrition counseling and the intensive nutrition counseling group. The difference for the percent of weight loss (%) at 12 months from baseline between two groups will be calculated, and the difference is tested using Student t-test. If the distribution for the percent of weight loss (%) violates the normality assumption, the non-parametric Wilcoxon rank-sum test will be used for sensitivity analysis. In addition, the percent of weight loss (%) at 1, 3, 6, 12 and 18 months will be analyzed using the generalized estimating equations (GEE) or mixed effects model to examine whether there is a difference between the two groups over time.

The repeated measures will be collected at baseline and each follow-up time points (1, 3, 6, 12, 18 months). All patients who had surgery and completed at least one baseline and

one follow-up (at any time point) measurement will be included. To estimate the difference between groups in change at each time points from baseline, the generalized estimating equations (GEE) or mixed effects model will be applied including time-by-group interaction term with the main effects. GEE method allows the inclusion of all participants, regardless of whether they have missing data at any follow-up time points, and will be adopted to take into account the within-patient correlation. The following effects will be estimated using GEE or mixed effects model:

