- 1) differences in the percent of weight loss (%) between the two groups
- 2) whether the percent of weight loss (%) change over time within each group
- 3) whether there are differences in the percent of weight loss (%) changes over time between the two groups.

Missing data are expected due to drop outs and missed visits. Although substantial effort will be employed to minimize the missing data, it is inevitable that some missing data will occur. Various statistical analyses will be employed to perform statistical inferences that properly account for statistical uncertainty due to missingness. The percent of weight loss (%) is a subject-level variable and missing assessments would influence tests relative to treatment-by-time interactions. The primary analysis described above will be performed using all data. No patients will be deleted from the analysis because of partial data. To assess the sensitivity of results, weight loss will be analyzed using:

- 1) All patients regardless of missing data
- 2) Only patients who participated in all assessment visits and have no missing data
- 3) Rubin's multiple imputation

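### FAS rule 4 removes randomised patients from the primary analysis for events after enrolment, and no stated analysis clearly brings them back

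*SAP*

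**What the plan says.** SAP section III.3.1 builds the FAS from the randomised subjects and then lists four exclusions. The fourth is "Subjects diagnosed with other severe diseases affecting weight or receiving additional treatment (ex. Surgery, chemotherapy, etc.) after enrollment". Section V states: "The Full Analysis Set will be used for the primary efficacy analyses".

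The supportive set is nested in the primary one. Under III.3.2, "PPS consists of data from subjects included in FAS", restricted further by completed counselling and adherence.

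Three other statements in section V bear on who is analysed:

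- The repeated-measures paragraph admits "All patients who had surgery and completed at least one baseline and" one follow-up measurement. It names no analysis set.
- The missing-data paragraph says "The primary analysis described above will be performed using all data" and "No patients will be deleted from the analysis because of partial data".
- The first sensitivity analysis is "All patients regardless of missing data".

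On blinding, section I says: "This study is a double-blind, parallel-assigned, randomized, prospective controlled trial".

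**The concern.** Rule 4 selects the primary set on what happens to patients after they enter the trial. Its first limb, severe disease affecting weight, is tied to the primary outcome. Its second limb, additional treatment, is not limited to conditions that affect weight. The SAP does not say when randomisation falls relative to enrolment. For any event after randomisation, the primary comparison no longer fully follows the randomised allocation.

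The rule also has no end date, although follow-up runs to 18 months. As written, an event at month 15 removes a patient whose 12-month weight is already on file. That patient has no missing data, so imputation is no remedy.

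If the two counselling groups differ in how often these events occur or are recorded, unlike patients leave the two arms and the difference in mean weight loss shifts. Without an analysis that keeps them, a reader cannot check whether this happened.

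**Working it through.** **Does any stated analysis restore rule 4 patients?**

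| Analysis | Restores them? |
|---|---|
| Per-Protocol Set (III.3.2) | No. It is a subset of the FAS and inherits rule 4. |
| Missing-data wording and the first sensitivity analysis (V) | Not clearly. The paragraph concerns dropouts and missed visits and does not mention rule 4. |
| Complete-case analysis and multiple imputation (V) | No. They deal with missing assessments, not with patients excluded by definition. |
| Repeated-measures inclusion rule (V) | Unclear. It can be read as wider than the FAS or as a data condition within it. |

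On the wide reading of the last row, the 12-month t-test and the GEE or mixed model use different sets without saying so. On the narrow reading, nobody is restored.

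**The plan's own figure (section IV).** With a difference of 2 points, SD 5.407 and two-sided alpha 0.05, the noncentral t calculation needs 115.7, so 116 per group, with power 0.801. Then 116/0.9 = 128.9, so 129 per group and 258 in total. The sample size reproduces and is not in question. The standard error is 5.407 × √(2/116) = 0.710.

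**Assumed inputs.** The SAP gives no event rates, so everything below is hypothetical: event rate e = 5% or 10%, extra loss among patients with an event L = 5 or 8 points, and q = the share of events that rule 4 excludes.

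**Route A: no true effect, unequal exclusion.** The mean extra loss left in an arm is e(1−q)L/(1−eq). The bias is its value at q1 minus its value at q2, with q1 = 0.5 or 0.7 in one arm and q2 = 0.9 or 1.0 in the other (16 combinations).

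- Smallest (e = 0.05, L = 5, 0.7 v 0.9): 0.075/0.965 − 0.025/0.955 = 0.0777 − 0.0262 = 0.05.
- Largest (e = 0.10, L = 8, 0.5 v 1.0): 0.40/0.95 − 0 = 0.42.
- Median of the 16: 0.16, which is 0.23 standard errors (0.162/0.710).

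With 116 per group and SD 5.407, type I error is 5.1% (smallest), 5.6% (median) and 9.1% (largest). Allowing for the smaller groups and the larger SD that these scenarios imply, the median becomes 5.5% and the largest 8.6%. Either way, 12 of the 16 combinations stay below 6%. If the median bias acts against the planned effect, power falls from 80.1% to 73.2%.

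With a milder gap of 85% v 95%, the bias is 0.03–0.09 points and type I error is at most 5.2%.

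**Route B: perfect blinding, every event excluded, event rates differ by arm.** The FAS omits (e1−e2)L from the group difference:

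- 5% v 3%: 0.02 × 5 = 0.10 to 0.02 × 8 = 0.16 points.
- 10% v 5%: 0.05 × 5 = 0.25 to 0.05 × 8 = 0.40 points.

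**No bias.** If exclusions are equal in share and alike in kind, the bias is 0.

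**The case against.** The strongest reply is that the repeated-measures rule, on its plain words, already covers a wider population for the same outcome, including month 12, and needs only a sentence naming its set. That reading is possible. But section V opens by assigning primary efficacy analyses to the FAS, and nothing says that rule 4 is lifted. This narrows the point without removing it.

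The second reply is that the trial is described as double-blind, so a gap of 50–70% against 90–100% in exclusion is hard to credit, and the milder gap is negligible. This largely stands for Route A: blinding, if kept, limits differential detection. The median of the combinations reflects which values were chosen and is not an estimate. Blinding does not, however, prevent counselling from changing how often the events occur.

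Third, Route B may describe a different question, namely the effect among patients free of such events, which the sponsor may want. The SAP does not say so. A set selected on post-randomisation events does not in general give a randomised comparison for that question either. It remains true that nothing in the SAP suggests counselling changes the need for surgery or chemotherapy, and that the assumed rates have no source.

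Finally, rules 1 to 3 also remove randomised patients, so changing rule 4 alone does not produce a full as-randomised set. That is correct; those rules are outside this point.

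**Conclusion.** The point holds. The SAP conditions its primary set on post-enrolment events linked to the outcome, and no stated analysis clearly keeps those patients. Confidence is high for that reading of the text, but not for any size of bias.

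The bias depends on event rates and exclusion patterns that the SAP does not give. Under the assumptions shown it runs from nil or negligible to roughly 0.4 points, a fifth of the planned difference (0.42/2 = 21%), and the upper end needs a marked imbalance between arms. This should be fixed: the defect lies in the definition of the primary population, and the repair is cheap.

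**What to change.** Remove rule 4 from the FAS and apply it only to the Per-Protocol Set or to a labelled sensitivity analysis. Include weights recorded after such events, where available, in the randomised arm. Report the number and type of rule 4 events by arm. State that the 12-month t-test and the GEE or mixed model use this same set.

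If the sponsor keeps rule 4 in the FAS, the minimum is an added, labelled analysis of the primary outcome without it, together with the counts by arm. The set used by the GEE or mixed model should still be named.

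The cost is a wording change, provided these patients are still weighed at scheduled visits, which the SAP does not say. The downside is added variability. Suppose the SD of 5.407 does not already include such patients. Keeping all of them gives SD = √(5.407² + e(1−e)L²) with 116 per group; excluding them gives SD 5.407 with 116(1−e) per group. Power for a 2-point difference is then:

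| e, L | SD if kept | Kept | Excluded | Change (points) |
|---|---|---|---|---|
| 5%, 5 | 5.516 | 78.5% | 78.0% | +0.5 |
| 5%, 8 | 5.681 | 76.1% | 78.0% | −1.9 |
| 10%, 5 | 5.611 | 77.1% | 75.8% | +1.3 |
| 10%, 8 | 5.916 | 72.7% | 75.8% | −3.1 |

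If only half of these patients have a 12-month weight, the change lies between 2.1 points lower and 0.5 points higher.

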#### **2) Per-Protocol Set (PP set)**

PPS consists of data from subjects included in FAS who received all nutrition counseling and completed the study per protocol without major violation.

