## IV. Sample size considerations

The primary objective is to clarify the difference for the percent of weight loss (%) at 12 months after surgery between the simple nutrition counseling and the intensive nutrition counseling group. The percent of weight loss (%) in the simple nutrition counseling group would be about 10% with standard deviation of 5.407% [reference]. We expected that the intensive nutrition counseling group would reduce by 20% in simple nutrition counseling group, which would result in a percent of weight loss(%) of 8% in the intensive nutrition counseling group.

We calculated that 116 patients in each group would provide a power of 80% to determine the difference for percent of weight loss (%) in intensive nutrition counseling group compared to the simple nutrition counseling group (8% vs. 10%) with a standard deviation for both groups of 5.407%. The comparison will be made using a two-sided, two-sample equal-variance t-test, with a significance level of 0.05. After considering 10% loss to follow-up, we determined the total enrollment of 258 patients (129 in each group). An interim analysis was not planned.

[reference]: Ryu K, Bae J, Kim E, An JY, Choi M, Lee JH, et al. *Long-term effect of simplified dietary education on the nutritional status of patients after a gastrectomy*. *PLoS One* (2021) 16(5):E252168. doi: 10.1371/journal.pone.0252168

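### Does requiring full receipt of counselling tilt the Per-Protocol Set towards the intensive arm?

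*SAP*

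**What the plan says.** SAP section III.3, item 2 (Per-Protocol Set), limits the set to "subjects included in FAS who received all nutrition counseling and completed the study per protocol without major violation". The wording is the same for both arms.

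Section V fixes the roles of the two sets: "The Full Analysis Set will be used for the primary efficacy analyses, and the Per-Protocol set will be used for supportive efficacy analyses". Section III.3, item 1 likewise assigns the primary outcome to the FAS. The FAS has a much weaker counselling condition than the PPS. On that point it removes only "Subjects who have never received the nutrition counseling during the study period", so partial attenders stay in the primary analysis in both arms.

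The SAP does not say how many sessions either arm has, when they take place or what they contain.

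**The concern.** Receipt of counselling is observed after randomisation and depends on patient behaviour. If the intensive arm has more sessions, a rule demanding all of them would exclude more patients there than in the simple arm. If those who miss sessions also tend to lose more weight, whatever the counselling does, the PPS would compare well-selected intensive patients with nearly unselected simple patients. It could then show a benefit where none exists, and that result might be cited as confirming the primary analysis or as rescuing a negative one. In this trial the amount of counselling may itself be the treatment contrast, so the point deserves a check.

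**Working it through.** **Design figures (SAP section IV).**
- Simple arm: "The percent of weight loss (%) in the simple nutrition counseling group would be about 10% with standard deviation of 5.407"%.
- Intensive arm: 8%, so the planned difference is 10 − 8 = 2 percentage points.
- Test: "two-sided, two-sample equal-variance t-test, with a significance level of 0.05".
- 116 per arm for 80% power; 129 per arm (258 in total) after 10% loss.

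These reproduce. The normal approximation gives 2 × (1.960 + 0.842)² × (5.407/2)² = 114.7, so 115 per arm. The exact t-test gives 115.7, so 116, with power 80.1%. Then 116/0.9 = 128.9, so 129. The concern disputes none of these figures.

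**Size of a possible PPS bias.** The SAP gives neither session counts nor expected attendance, so the following inputs are assumptions:
- no true effect;
- 95% of the simple arm qualifies;
- 80%, 70% or 60% of the intensive arm qualifies;
- correlation r between the tendency to attend and lower weight loss;
- the least adherent patients are the ones removed.

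If a fraction p qualifies, the mean of the standardised attendance tendency among those kept is m(p) = φ(c)/p, with c the cut-off that keeps p. Bias towards intensive = r × 5.407 × [m(intensive) − m(simple)].

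m(0.95) = 0.1086, m(0.80) = 0.3500, m(0.70) = 0.4967, m(0.60) = 0.6439.

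Example, 60% and r = 0.3: 0.3 × 5.407 × (0.6439 − 0.1086) = 0.87 points. The standard error is 5.407 × √(1/(116 × 0.60) + 1/(116 × 0.95)) = 0.828. The shift is 0.868/0.828 = 1.05 standard errors, so the two-sided type I error is 18.2%.

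| Intensive qualifying (simple 95%) | r = −0.2 | r = 0 | r = 0.1 | r = 0.2 | r = 0.3 |
|---|---|---|---|---|---|
| 95% | 0 | 0 | 0 | 0 | 0 |
| 80% | −0.26 | 0 | 0.13 | 0.26 | 0.39 |
| 70% | −0.42 | 0 | 0.21 | 0.42 | 0.63 |
| 60% | −0.58 | 0 | 0.29 | 0.58 | 0.87 |

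Type I error is 5.3% at 80% with r = 0.1, 5.8% at 70% with r = 0.1, 8.3% at 70% with r = 0.2, and 18.2% at 60% with r = 0.3. The last case is 0.868/2 = 43% of the planned difference and needs both extreme assumptions at once.

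As another illustration, 1 session against 5 with 95% attendance at each gives 95% against 0.95⁵ = 77% qualifying, and a bias of 0 to 0.45 points for r = 0 to 0.3.

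**What the table rests on.** A bias needs two things together: unequal completion and a non-zero r. The SAP supports neither.
- Unequal completion is inferred from the words simple and intensive. The arms might differ in session number, but also in depth or content at the same visits, and then the rule is equally demanding in both.
- The sign of r is open. Conscientious patients may both attend and eat better (r positive). Patients losing weight may attend more because they are worried (r negative), which counts against intensive counselling.
- The model leaves out the PPS's other condition, completion of the study without major violation. Follow-up runs to 18 months, so that condition removes poor attenders from both arms and could narrow the contrast.

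**Consequence for the trial's conclusion.** The primary comparison uses the FAS, which keeps partial attenders. None of the biases in the table enters it. The SAP has no decision rule that uses the PPS.

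**The case for a change.** The strongest case is that a per-protocol exposure rule usually asks the same of both arms, whereas here the intervention itself may differ in amount. If the chance of attending each session is similar, an all-sessions rule becomes stricter as sessions are added, and more sessions is a natural reading of intensive. The SAP defines no major violations and plans no counts or baseline comparison of PPS members by arm. The FAS already drops some patients after randomisation, so the PPS adds a second selection. Bias in either direction would weaken the PPS as support.

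Part of this stands. The PPS is not protected by randomisation, and agreement between PPS and FAS is weak evidence. Reporting PPS numbers and baseline characteristics by arm would be good practice. But these statements hold for nearly every per-protocol analysis and do not show that this SAP fixes something wrongly. The step from a possible imbalance to a stated one needs a session schedule, which would normally sit in the protocol, not shown here. The step to a stated direction needs an attendance–outcome link that the SAP does not give.

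The alternatives are not clearly better. Dropping the exposure condition removes what gives the PPS its purpose. Requiring a month-12 weight instead is another post-randomisation filter. A complier-average estimate based on all-or-nothing attendance assumes that partial attenders gain nothing from the sessions they attended, which is doubtful for counselling and harder still to justify with two active arms.

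**Conclusion.** This is not an error in the plan. The rule is a conventional per-protocol definition, worded alike for both arms and confined to a supportive role. That it is harder to meet in the intensive arm, and that it favours that arm, are both inferences. Under assumed completion rates and correlations the PPS bias could be anything from zero to 0.87 points towards intensive counselling, or of opposite sign; the document gives no basis for choosing a value. The effect on the primary FAS result is nil. The worry about rescuing a negative trial concerns possible later misquotation, since the SAP contains no such provision. The conclusion would need another look if the protocol showed markedly different session numbers by arm, but even then only the weight given to a supportive analysis would change.
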